14.1.4 Sample Size Estimation

Little data exists on the incidence of arrhythmias that occur over an extended period of time following AMI and monitoring strategies for this type of assessment have not been optimized in a clinical trial setting. The primary goal of our study is to characterize the occurrence of arrhythmias in this patient population for 14 days post-AMI and to determine the feasibility of using ambulatory patch ECG monitors to capture this data. These data should be regarded as exploratory with the objective of identifying a meaningful clinical end point that can be easily measured in future, pivotal studies that are adequately powered to detect differences across treatment groups.

Estimating a drop-out rate of approximately 50%, we will need to enroll up to 160 patients in order to obtain a final total sample size of 80 patients. A final sample size of 80 patients will provide 80% power to detect a 37% reduction in INF/VV assuming an SD of 10%, a 24% increase in MSI assuming an SD of 20% and a 39% reduction in Troponin AUC with an SD of 60%. Equal variance was assumed among groups with an unbalanced allocation of patients to placebo (n=20) and combined FDY-5301 treatment groups (n=60).

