14.1.6 General Analysis of Safety and Efficacy Outcomes

Analysis of the primary safety outcome: characterize the number and incidence rate of serious arrhythmias that occur during a 14-day interval in this patient population. No hypothesis will be tested and data will be descriptive in nature only. A more detailed analysis strategy will be outlined in the SAP.

Analysis of exploratory secondary efficacy outcomes: For all variables with a continuous outcome including infarct size relative to the VV, MSI, absolute MI size, cardiac function, biomarkers of cardiac injury and cardiac troponin levels, a single pairwise comparison to analyze differences between all three FDY-5301 groups (combined) and placebo will be used. An unpaired Student's T test will be used for the pairwise comparison if the data are normally distributed and a Mann-Whitney rank test will be used for nonparametric data. Each group will then be tested using a one-way analysis of variance (ANOVA) to obtain a common variance followed by a Dunnett's post-test to separately compare each FDY-5301 dose group to placebo.

For categorical outcome including ST-segment resolution and incidence of all-cause and cardiac related mortality or morbidity, odds ratios comparing each FDY-5301 treatment group with placebo will be calculated.

Physical examination data from baseline, post-study and **medical history** data at baseline and peri-procedural arrhythmia data will be listed by patient. All clinical safety and tolerability data will be listed for each subject. **Laboratory values** will be calculated as group mean data and presented in shift tables. Comments as to the clinical significance of out of range values will be listed separately. **Adverse event** data will be summarized by group, visit, severity, and possible relationship to the study drug.

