11.4.2.5 Serum Levels of Troponin

The troponin AUC₀₋₄₈ will be derived from the serum levels of troponin collected at the following timepoints: Predose, 4, 12, 24 and 48 hours post-study drug. AUC₀₋₄₈ will be calculated using the linear trapezoidal method. Where possible, the derivation will be carried out using actual post-dose times recorded. If actual times are missing, nominal times may be used with sponsor approval.

Summary statistics (also including geometric means and geometric coefficient of variation [CV] %) for the serum levels will be produced by each treatment group and the combined FDY-5301 group for the derived AUC₀₋₄₈. The summary statistics for troponin AUC₀₋₄₈ will be presented in a similar way.

The derived AUC₀₋₄₈ will be logarithmically transformed, and an unpaired Student's T-test will be used analyze its differences between all three FDY-5301 groups (overall) and placebo.

The logarithmically transformed AUC₀₋₄₈ from each group will then be tested using a one-way ANOVA to obtain a common variance followed by a Dunnett's post-test to separately compare each FDY-5301 dose group to placebo.

The arithmetic least squares means of the treatment differences will be back-transformed to provide the geometric means and its 95% confidence interval.

The same summarization and statistical analyses will be repeated by baseline TIMI flow (grade 1 and lower, or, grade 2 and 3) and infarct type (anterior or other).

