11.4.2.6 Plasma Biomarkers of Cardiac Injury, Inflammation, and Remodeling

The plasma biomarker C_{max} and AUC₀₋₄₈ will be derived from the plasma biomarker levels collected at the following timepoints: Predose, 1, 4, 12, 24 and 48 hours post-study drug. AUC₀₋₄₈ will be calculated using the linear trapezoidal method. Where possible, the derivation will be carried out using actual post-dose times recorded. If actual times are missing, nominal times may be used with sponsor approval. Maximum deviation defined as the largest magnitude shift (or absolute change) from baseline will be derived.

Summary statistics (also including geometric means and geometric CV%) for each plasma biomarker concentration will be produced by each treatment group and the overall FDY-5301 group for the values and its changes from baseline. The baseline is defined as the last actual value obtained prior to study drug infusion.

For each of these plasma biomarker concentrations, a single pairwise comparison will be performed by timepoint to analyze change from baseline value between all three FDY-5301 groups (overall) and placebo. An unpaired Student's T-test will be used for the pairwise comparison if the data are normally distributed and a Mann-Whitney rank test will be used for nonparametric data. Normality will be assessed based on the Shapiro-Wilk test at the 5% level.

Each group will then be tested using a one-way ANOVA to obtain a common variance followed by a Dunnett's post-test to separately compare each FDY-5301 dose group to placebo.

The logarithmically transformed C_{\max} , AUC_{0-48} and maximum deviation from each group will be tested using a one-way ANOVA to obtain a common variance followed by a Dunnett's post-test to separately compare each FDY-5301 dose group to placebo.

The arithmetic least squares means of the treatment differences will be back-transformed to provide the geometric means and its 95% confidence interval.

The same summarization and statistical analyses for plasma biomarker concentrations and parameters will be repeated by baseline TIMI flow (grade 1 and lower, or, grade 2 and 3) and infarct type (anterior or other).

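### SAP 11.4.2.6 gives biomarker Cmax, AUC0-48 and maximum deviation no pooled FDY-5301 versus placebo comparison, although Protocol 14.1.6 sets one for all continuous outcomes, and SAP 13 does not declare this

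*SAP*

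**What the plan says.** Protocol 14.1.6 sets one rule. Its scope is "For all variables with a continuous outcome including infarct size relative to the VV, MSI, absolute MI size, cardiac function, biomarkers of cardiac injury" and troponin. For these, "a single pairwise comparison to analyze differences between all three FDY-5301 groups (combined) and placebo will be used". A one-way ANOVA comes next, "followed by a Dunnett's post-test to separately compare each FDY-5301 dose group to placebo".

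SAP 11.4.2.6 treats the biomarkers in two ways:

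- **Levels at each timepoint:** "a single pairwise comparison will be performed by timepoint to analyze change from baseline value between all three FDY-5301 groups (overall) and placebo". ANOVA and Dunnett follow, so both protocol steps are present.
- **Derived summaries** (log Cmax, AUC0-48, maximum deviation): the values "and maximum deviation from each group will be tested using a one-way ANOVA to obtain a common variance", then Dunnett for each dose against placebo. No pooled test is given.

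SAP 11.4.2.5 handles the log-transformed troponin AUC0-48 differently. An unpaired Student's "T-test will be used analyze its differences between all three FDY-5301 groups (overall) and placebo", and ANOVA with Dunnett follows. SAP 11.4.2.1 (infarct size) and 11.4.2.4 (cardiac function) also keep both steps.

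SAP 4 undertakes to identify considerations that differ substantially from the protocol. SAP 13 lists the person-time adjustment, the interim scope and the summaries by TIMI flow and infarct location. It says nothing about the biomarker summaries.

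**The concern.** Two log-transformed trapezoidal AUCs over the same 48 hours, in adjacent SAP sections, follow different rules, and no reason is given. The sample size in Protocol 14.1.4 and SAP 9 sets 20 placebo patients against 60 on any dose of FDY-5301, so the pooled contrast is the one around which the design is organised.

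The pooled tests that remain are run separately at each timepoint, on correlated measurements. The derived summaries reduce each profile to one number, and that is where the pooled contrast is missing. If it is not prespecified, a pooled Cmax or AUC0-48 result in the study report would be an addition to the plan. If the drug acts about equally at all three doses, the dose-by-dose estimates are also less precise than the data allow.

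**Working it through.** **Inputs.** 20 placebo versus 60 pooled (Protocol 14.1.4, SAP 9); randomization 1:1:1:1 (SAP 7), so 20 per arm at N = 80 and 40 per arm at N = 160. The documents give no biomarker effect or SD, and no alpha or sidedness for the power statement. Two-sided 5% is assumed below, with a one-sided check.

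**1. The plan's own figure.** Power comes from the noncentral t with noncentrality d / sqrt(1/n1 + 1/n2). For troponin, d = 39/60 = 0.65 if both figures are percentages of the control mean. The standard error factor is sqrt(1/20 + 1/60) = 0.258, so the noncentrality is 0.65/0.258 = 2.52. With 78 df, power is 80.3% one-sided at 5% and 70.1% two-sided. The stated 80% is thus reproduced for 20 versus 60 on a one-sided reading, which confirms that the pooled contrast was the basis. INF/VV and MSI cannot be checked without control means, which are not given.

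**2. Assumed biomarker effect.** Take the effect at which the pooled two-sided test has 80% power: d = 0.73 SD (0.732/0.258 = 2.84, critical value 1.99). Let it be equal in all doses.

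**3. Dunnett with the same data.** Each dose contrast has factor sqrt(2/20) = 0.316 and noncentrality 0.732/0.316 = 2.32. The simulated two-sided Dunnett critical value is about 2.39 to 2.40 (76 df).

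| Setting (equal effects) | Pooled | A given dose | At least one dose |
|---|---|---|---|
| 20 per arm, two-sided, 0.73 SD | 80% | 47% | 72% |
| 20 per arm, one-sided, 0.65 SD | 80% | 49% | 74% |
| 40 per arm, two-sided, 0.73 SD | 98% | 82% | 96% |

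At 20 per arm, the effect that gives 80% power for a single dose is 1.03 SD, against 0.73 SD pooled (two-sided). The 40-per-arm row is relevant because the Synopsis defines evaluable by complete arrhythmia and infarct-size data, whereas AUC0-48 needs only samples to 48 hours. The number available may therefore exceed 20 per arm.

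**4. Unequal effects.** With illustrative effects of 0.25, 0.5 and 1.0 SD (mean 1.75/3 = 0.58) at 20 per arm, two-sided, Dunnett finds at least one dose in about 79% of trials. The pooled t-test is significant in about 58%.

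**5. Interval width, one dose versus pooled.** Unadjusted: 0.316/0.258 = 1.22. With Dunnett adjustment: (2.39 × 0.316)/(1.99 × 0.258) = 1.47. SAP 11.4.2.6 promises a 95% interval without saying whether it is adjusted.

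**The case against.** The protocol never defines biomarker Cmax, AUC0-48 or maximum deviation. It defines levels at timepoints (Protocol 12.2.5), and for those the SAP keeps the full sequence. Troponin AUC0-48 is a named secondary outcome with a power target, so it might deliberately be treated differently. SAP 4 requires only substantial differences to be identified. All of this stands and limits the weight of the point. It does not remove it: the protocol's rule covers all continuous variables, and neither document gives a reason for the exception.

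A reader might infer more than the documents support, in three ways:

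- **That a powered comparison has been lost.** The sample size rests on INF/VV, MSI and troponin AUC, and SAP 11.4.2.1 and 11.4.2.5 keep pooled tests for them. No biomarker was powered.
- **That Dunnett is the departure, or is generally the weaker test.** The protocol itself specifies Dunnett. Step 4 shows that it can be stronger when the effect rises with dose, and the doses here span a fourfold range.
- **That a uniform effect would usually be missed.** The 47% is for one named dose. The chance that at least one dose is significant is 72% against 80% pooled, or 96% against 98% at 40 per arm.

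**Conclusion.** The omission is real and undeclared, and it looks like a drafting gap rather than a choice. Its consequence is modest. Three SAP-derived, exploratory summaries lack the pooled contrast that the protocol's general rule gives them, while the timepoint comparisons keep it. Under equal effects the loss at 20 per arm is 33 percentage points for a given dose (80 − 47) but 8 for any dose (80 − 72). At 40 per arm it is 16 and 2 points. A single-dose interval is 1.22 times as wide as the pooled one, or 1.47 times with Dunnett adjustment. All the power figures rest on an assumed effect size and alpha, and the direction of the power comparison reverses under a sufficient dose gradient. The case for the change is a prespecified and more precise overall estimate, consistent with the protocol and with the adjacent SAP section. No main conclusion of the trial is at risk.

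**What to change.** In SAP 11.4.2.6, before the Dunnett step, add an unpaired t-test of overall FDY-5301 versus placebo on log Cmax and log AUC0-48, with the back-transformed ratio and its 95% CI, as in SAP 11.4.2.5. Keep Dunnett by dose.

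Do the same for maximum deviation, but first settle its definition. The SAP describes it as the largest shift in magnitude or as an absolute change. If it is an absolute (positive) value, the log scale can be used. If it is signed, negative values have no logarithm and it should be compared untransformed.

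If the omission was intended, list it in SAP 13 with a reason.

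The text change is small. The cost is one more exploratory test per parameter, repeated in the ITT and PP populations (SAP 11.4) and by TIMI flow and infarct type: 2 × (1 + 2 + 2) = 10 per parameter, or 30 per biomarker over the three parameters. None is confirmatory and they should be labelled so.

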11.4.3 Exploratory Analysis (Safety)

Incidence Rate of New Onset Atrial Fibrillation

The exploratory outcome for this study will be the combined number and incidence rate of new onset atrial fibrillation for 14 days post-study drug. The combined number of events in each treatment group will be calculated along with incidence rate defined as the number of events divided by the total person-time within each treatment group (or the overall FDY-5301 group), expressed as a percentage.

The number of new onset atrial fibrillation and new onset atrial fibrillation incidence rates will be summarized by treatment group and the overall FDY-5301 group.

The incidence rate ratio of each active treatment group (and overall) against the placebo group will be calculated.

The summarization will be presented by 2 separate periods within the 14-day monitoring duration, and also as overall. Period 1 will be the first 48 hours since the start of PCI procedure and period 2 will be the remaining time of 14-day monitoring duration.

11.5 Safety and Tolerability Assessments

All safety analyses will be performed with the safety population.

11.5.1 Adverse Events

The study specifically recruits STEMI patients; therefore the myocardial infarction (MI) itself will not be characterized as an AE. However, complications arising as a consequence of the MI, for example, an emergent or worsening heart failure, death, or arrhythmias will be specifically documented as adverse events in the CRFs.

A baseline sign and symptom is defined as an AE that starts after the patient has provided written informed consent and that resolves prior to the first dosing occasion, or an AE that starts prior to the first dosing occasion and does not increase in severity after dosing. A treatment-emergent AE (TEAE) is defined as an AE that occurs postdose or that is present predose and becomes more severe postdose.

All AEs will be listed. The TEAEs will be summarized by treatment, severity, and relationship to the study drug. The frequency (the number of TEAEs, the number of patients experiencing a TEAE, and the percentage of patients experiencing a TEAE) of TEAEs and serious TEAEs will be summarized by treatment, and by MedDRA system organ class and preferred term. The summary and frequency TEAE tables will be presented for all causalities and for those TEAEs considered related to the study drug (those that have a relationship of probable or possible). A subset of serious adverse events and adverse events which are cardiac related, including the development of heart failure, will also be presented as summary tables. For any AEs that change severity ratings the AE will be included only once under the maximum severity rating in the summaries. Any life-threatening, severe or serious AEs will be listed.

Onset times postdose are calculated from the start of study drug infusion.

11.5.2 Clinical Laboratory Parameters

Clinical chemistry (including thyroid function tests) and hematology data will be summarized by treatment group. Changes from baseline will be calculated. Shift tables from baseline will be presented. In addition, all clinical chemistry and hematology data outside the clinical reference ranges will be listed by parameter and treatment.

Values for any clinical chemistry and hematology values outside the clinical reference ranges will be flagged on the individual patient data listings.

11.5.3 Vital Signs

Vital signs values outside the clinical reference ranges will be flagged on the individual patient data listings.

The vital signs data will be summarized by treatment group, together with changes from baseline. Figures of mean vital signs and mean change from baseline profiles will be presented by treatment. Repeat and unscheduled readings will be handled as defined in Section [11.1.2](#).

11.5.4 Incidence of Mortality

The incidences of all-cause and cardiac mortality out to 6 months post PCI will be listed and tabulated by treatment group.

11.5.5 Other Safety Assessments

All other safety assessments not detailed in this section will be listed but not summarized or statistically analyzed.

11.5.6 Safety and Tolerability Statistical Methodology

No inferential statistical analyses are planned.

11.6 Pharmacokinetic Assessment

11.6.1 Pharmacokinetic Analysis

The following PK parameters will be determined where possible from plasma iodide concentrations using non-compartmental methods performed using Phoenix WinNonlin (Version 6.4 or higher):

Parameter	Definition
AUC _{last}	area under the concentration-time curve from time 0 to the time of the last observed quantifiable concentration (T _{last}), calculated using the linear trapezoidal rule for increasing concentrations and the logarithmic rule for decreasing concentrations
AUC _{inf}	area under the concentration-time curve extrapolated to infinity calculated using the following equation: $AUC_{inf} = AUC_{last} + C_t/Kel$ where C _t is the last observed quantifiable concentration and Kel is the terminal elimination rate constant.
C _{max}	maximal observed plasma concentration
T _{max}	time when maximal concentration is achieved
T _{last}	time of last quantifiable concentration
Kel	apparent terminal elimination rate constant
T _{1/2}	apparent terminal elimination half-life, calculated as natural log (ln)(2)/Kel
CL	total body clearance
V _z	volume of distribution during the terminal elimination phase
V _{ss}	volume of distribution at steady-state

Additional PK parameters may be determined where appropriate. If the IV bolus model is used (refer to last bullet point in Section 11.6.4), then C₀ (back-extrapolated concentration at time zero) may be calculated by excluding the observed predose concentration value and then using a log-linear regression of the first 2 postdose data points to back-extrapolate to the concentration at time 0.

Pharmacokinetic analysis will, where possible, be carried out using actual postdose times recorded in the raw data. If actual times are missing, nominal times may be used with sponsor approval.

Concentrations will be used as supplied by the analytical laboratory for PK analysis. The units of concentration and resulting PK parameters, with amount or concentration in the unit, will be presented as they are received from the analytical laboratory.

The dose level of FDY-5301 (sodium iodide) will be converted to its free base equivalent for PK analysis if the analytical laboratory reports the free base concentration.

C_{max}, T_{max}, and T_{last} will be obtained directly from the plasma concentration-time profiles.

For multiple peaks, the highest postdose concentration will be reported as C_{max}. In the case that multiple peaks are of equal magnitude, the earliest T_{max} will be reported.

11.6.2 Criteria for Handling Concentrations Below the Limit of Quantification in Pharmacokinetic Analysis

- Concentration values that are below the limit of quantification (BLQ) will be set to zero, with defined exceptions as follows;
 - Any embedded BLQ value (between 2 quantifiable concentrations) and BLQ values following the last quantifiable concentration in a profile will be set to missing for the purposes of PK analysis.
 - If there are late positive concentration values following 2 BLQ concentration values in the apparent terminal phase, these values will be evaluated. If these values are considered to be anomalous, they will be set to missing.
 - If an entire concentration-time profile is BLQ, the profile will be excluded from the PK analysis.
 - If a predose concentration is missing, it may be set to zero with sponsor approval.

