4.2 Secondary Outcomes

Infarct size parameters will be assessed by CMR at 72 +/- 24 hours and 3 months; the following will be compared between groups; infarct size as a proportion of ventricular volume (INF/VV), myocardial salvage index (MSI) and absolute MI size.

- The proportion of patients with ST-segment resolution at 4 hours post study drug
- Serum levels of troponin calculated as AUC 0-48 hours post-study drug
- Persistent arrhythmias at 30 days and 3 months
- Measures of cardiac function by CMR including end-diastolic volume (EDV), end-systolic volume (ESV), fractional shortening (FS) and ejection fraction (EF).
- Serum biomarkers of cardiac injury, inflammation and remodeling
- Cardiac-related adverse events including the development of heart failure out to 3 months of follow up
- Incidence of all cause and cardiac mortality out to 6 months of follow up-to be assessed by phone call to patient or if

patient is unavailable, by medical records of physician/investigator.

Safety and Tolerability:

Physical examination including vital signs, laboratory measures to include clinical chemistry, hematology and thyroid function tests will be performed. Adverse Events (AEs) and Serious Adverse Events (SAEs) will be recorded.

12 lead ECGs will be performed at intervals at and post baseline.

Pharmacokinetics:

Plasma iodide levels will be measured in each patient. The concentration-time profile of plasma iodide will be derived for each of the groups. The pharmacokinetics of iodide will be described as area under the concentration versus time curve (AUC), the maximal concentration (C_{max}) and the time (T_{max}) when the maximal concentration is achieved. The terminal half-life ($T_{1/2}$), the total body clearance (CL), and the volume of distribution (V) will also be derived.

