10 DEFINITION OF ANALYSIS POPULATIONS

The **Intent-to-treat (ITT)** population will include patients who gave assent, full consent, abbreviated consent or waived consent and were randomized. This is the “full analysis set” of patients. Patients are included in the ITT population according to the treatment assigned.

The **Safety Population** will consist of all patients who received at least 1 dose of study drug (FDY-5301 or Placebo) and have at least 1 postdose safety assessment.

The **Per Protocol (PP)** population will be a subset of the ITT population and will include patients who gave informed assent/consent, were randomized, received any amount of study drug, underwent PCI, and underwent magnetic resonance imaging (MRI) at 72 ± 24 hours and 3 months.

The **PK Population** will consist of all subjects dosed with FDY-5301 and have at least 1 quantifiable postdose PK concentration.

The **PK/PP Population** will consist of all subjects who satisfy the criteria for both the PK and PP population.

All protocol deviations that occur during the study will be considered prior to database lock for their severity/impact and will be taken into consideration when patients are assigned to analysis populations. Details of patient assignment to the analysis populations will be listed.

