11.6.8 Pharmacokinetic/Efficacy Analysis

A scatterplot will be produced to evaluate potential correlations between the Iodide plasma AUC_{inf} and INF/VV at 3 months post-study drug.

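### The SAP derives iodide PK from total plasma iodide, without predose subtraction or a placebo summary; any quantifiable background would inflate AUCinf and half-life, most in relative terms at 0.5 mg/kg

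*SAP*

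**What the plan says.** SAP 11.6.1 sets the analyte and method: "The following PK parameters will be determined where possible from plasma iodide concentrations using non-compartmental methods". It adds: "Concentrations will be used as supplied by the analytical laboratory for PK analysis". The parameters include AUClast, AUCinf, Kel, T1/2, CL, Vz and Vss.

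The predose value is mentioned in two places. Under the optional IV bolus model, C0 may be "calculated by excluding the observed predose concentration value" and back-extrapolating from the first two postdose points (11.6.1). In 11.6.2: "If a predose concentration is missing, it may be set to zero with sponsor approval". Neither is a background correction. SAP 11.1.1 defines baseline and change from baseline in general, but 11.6 does not apply them to iodide, and protocol 12.1.1 and 14.1.7 contain no correction.

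The PK population in SAP 10 is "all subjects dosed with FDY-5301 and have at least 1 quantifiable postdose PK concentration", and SAP 11.6.7 runs all PK analyses on it. Protocol 4.2 says: "Plasma iodide levels will be measured in each patient. The concentration-time profile of plasma iodide will be derived for each of the groups". SAP 13, which lists changes from the protocol, does not mention leaving placebo out.

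On units, SAP 11.6.1 says that the sodium iodide dose will be "converted to its free base equivalent for PK analysis if the analytical laboratory reports the free base concentration".

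**The concern.** The measured substance is iodide, not a molecule unique to the study drug. Protocol 3.2 itself refers to orally administered iodide, and a pre-study-drug sample is drawn, so a patient may have measurable iodide before dosing. Used uncorrected, that background lies under every postdose sample. It matters most at 24 h and 48 h, when drug-derived iodide is lowest, and those two samples largely determine Kel and the extrapolated area.

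The same background is four times as large relative to 0.5 mg/kg as to 2.0 mg/kg. Even with perfectly dose-proportional kinetics, the lowest dose would show a longer half-life and lower clearance than the highest. A reader could take that for a property of the drug. Iodide acquired after dosing from any other source would not appear in the predose sample. Only the placebo group can show it, and that group has no planned summary.

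**Working it through.** The documents state no expected PK value, so there is no planned figure to reproduce. The check applies the SAP's own rules to a known profile with and without a background.

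**Inputs from the documents**
- Postdose samples at 2 min, 1, 4, 24 and 48 h, plus predose (protocol 12.1.1 and Table 2; the Day 3 list in 5.5.4 omits the 48 h PK sample and should be reconciled with these).
- Doses of 0.5, 1.0 and 2.0 mg/kg.
- AUC by the linear rule when rising and the log rule when falling; AUCinf = AUClast + Ct/Kel; T1/2 = ln 2/Kel (SAP 11.6.1).
- At least three points for Kel, preferably without Cmax (11.6.3.1). The last three (4, 24, 48 h) are used here.
- Limits: adjusted R² of at least 0.7 (11.6.3.2); AUCinf left out of the descriptive statistics above 30% extrapolation (11.6.4).

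**Assumptions, not in the documents**
- One compartment, dose-proportional: C(t) = D·exp(−kt) + b, with D = 1, 2, 4 for the three doses and k = ln 2 / true T1/2.
- The floor b is constant and stated as a share of the 0.5 mg/kg initial concentration. It is also the value at time 0.
- True T1/2 of 8 h, varied to 6 h and 12 h.

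**Worked case: T1/2 8 h, b = 0.05**
- Drug-derived iodide at 48 h is 2^(−6) = 0.0156 at 0.5 mg/kg and 4 × 0.0156 = 0.0625 at 2.0 mg/kg.
- Measured values are 0.0656 and 0.1125, so the floor is 0.05/0.0656 = 76% and 0.05/0.1125 = 44% of the last sample.
- AUCinf at 0.5 mg/kg is 15.38 against a true 11.53, ratio 1.33. At 2.0 mg/kg it is 49.94 against 46.10, ratio 1.08.

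**Results at true T1/2 8 h**

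| Floor | AUCinf, 0.5 mg/kg | AUCinf, 2.0 mg/kg | Apparent T1/2, 0.5 / 2.0 | CL, 0.5 / 2.0 |
|---|---|---|---|---|
| 0.25% | +1.7% | +0.4% | 8.3 / 8.1 h | −1.7% / −0.4% |
| 1% | +7% | +2% | 9.2 / 8.3 h | −6% / −2% |
| 5% | +33% | +8% | 12.6 / 9.4 h | −25% / −8% |

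If the better-fitting of three or four terminal points is used instead, the 5% row gives 12.0 / 9.3 h and the rounded AUCinf errors are unchanged.

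**Other half-lives, 5% floor:** AUCinf +45% and +12% (0.5 and 2.0 mg/kg) at T1/2 6 h; +23% and +6% at 12 h.

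**Would the SAP's limits catch it?** Over floors up to 10% and half-lives of 6 to 12 h, adjusted R² never fell below 0.76 and extrapolation stayed below 17%. Every profile would be accepted.

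**Effect of subtraction:** with a constant floor, subtracting the predose value restores the true parameters at every dose.

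**Unit rule:** CL = dose/AUCinf. Using the NaI dose with iodide concentrations multiplies CL and Vz by the molar mass ratio, 149.89/126.90 = 1.18, at every dose. The conversion factor is 126.90/149.89 = 0.847.

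**The case against.** The strongest objection is that the size has no anchor. The documents give no background level, half-life or LLOQ. If predose values are unquantifiable and nothing is acquired later, the bias is zero; at a floor of 0.25% it is under 3% for every half-life tried. This stands: the plan permits a bias but does not establish one.

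Four further inferences are tempting, and the documents do not support them.

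- *The AUCinf versus infarct-size plot is distorted.* SAP 11.6.8 plots "potential correlations between the Iodide plasma AUC_{inf} and INF/VV at 3 months post-study drug". A constant floor adds almost the same absolute amount at each dose (3.86, 3.83 and 3.84 at 0.5, 1.0 and 2.0 mg/kg in the worked case), so the points shift sideways together. Only a floor that differs between patients could disturb the plot, and nothing in the documents quantifies one.
- *Setting a missing predose value to zero biases the planned analysis.* Without subtraction, that value enters only the 0 to 2 min trapezoid. In the worked case the change is (2/60 × 0.05)/2 = 0.0008 out of 15.38, below 0.01%.
- *The free-base wording adds to the dose dependence.* The 18% is identical at every dose. The intent to match the dose to the measured substance is also fairly plain, although sodium iodide has no free base.
- *Placebo iodide is discarded.* Listings cover the ITT population (SAP 11.1), so values can still be seen. SAP 11.6.7 also speaks of summarising all reportable concentrations by treatment, which fits poorly with its own population sentence. Protocol 12.1.1 refers to dose groups, so 4.2 is not an unambiguous promise of a placebo profile.

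PK is also descriptive, with no formal test planned, and SAP 4 allows added analyses. That lowers the stakes. It does not answer the point, because a later correction would be chosen after the data were seen.

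**Conclusion.** The point holds conditionally. SAP 11.6.1 derives exposure, half-life and clearance from total iodide with no predose correction, and SAP 10 with 11.6.7 leaves placebo iodide out of the PK summaries. If predose iodide is quantifiable, AUCinf and T1/2 are overstated and CL understated. The relative AUCinf error at 0.5 mg/kg is about four times that at 2.0 mg/kg, while the absolute error is nearly equal.

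Under the assumptions above, the effect ranges from negligible to about a third of AUCinf at the lowest dose. Dose ordering survives: with a 5% floor and T1/2 8 h, the fourfold AUCinf range becomes 49.94/15.38 = 3.2-fold. The harm is therefore to descriptive half-life, clearance and apparent dose proportionality, not to any test or decision rule. The unit wording is a separate, minor matter.

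**What to change.** 1. In SAP 11.6.1, report baseline-corrected parameters (each concentration minus the patient's predose value, negatives set to zero) alongside the uncorrected ones.
2. Where the predose value is missing, report uncorrected parameters only, flagged. The set-to-zero option in 11.6.2 should not apply to corrected parameters: once subtraction is used, it would present an uncorrected patient as corrected.
3. Summarise placebo iodide concentrations by time point, and amend SAP 10 or 11.6.7 to allow it. Predose subtraction handles only a stable background; iodide acquired after dosing can be seen only in placebo patients.
4. As a separate wording change, replace the free-base condition with conversion of the NaI dose to iodide (× 0.847) whenever iodide concentration is reported.

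The cost is SAP wording and one extra set of outputs, with no new samples. The downside is that some corrected late values may fall near the LLOQ, leaving fewer usable points for the terminal slope. If background is negligible, the two sets will agree and the assumption will have been checked.
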